2.11.3 Adverse events by primary system organ class and preferred term

The number (n) and percentage (%) of patients with AEs (TEAEs/Post-treatment AEs) will be summarized in separate tables by primary SOC, PT by treatment group and “Active Total: Safety”, overall and by region (Japan/Non-Japan). Unless otherwise specified, primary SOCs will be sorted alphabetically and within each primary SOC, the PTs will be sorted by descending order of total frequency across “Active Total: Safety”. In the event of PTs with equal total frequencies, the relevant PTs will be sorted alphabetically. The number (n) and percentage (%) of patients with at least one AE, and with at least one AE in each primary SOC, and PT will be presented. Hence if a patient reported more than one AE with the same PT, the AE will be counted only once. Similarly, if a patient reported more than one AE within the same primary SOC, the patient will be counted only once at the SOC level.

The following AEs (TEAEs/Post-treatment AEs) will be summarized:

- All AEs.
- Most frequently reported (PT > 5% in any of the four treatment groups).
- By strongest relationship to study drug (only for Post-treatment AEs).
- By maximum severity.
- Leading to discontinuation of study drug.
- SMQ – Liver, diarrhea, muscle contractions, cardiac and orthopedic adverse events of special interest (AESIs) reported in the Program Compound Case Retrieval Sheet (CRS).

In addition, all AEs will be summarized by time interval, also presenting a summary of patients with at least one:

- AE.
- SAE.
- AE leading to discontinuation of the study drug.

2.11.4 Adverse events related to study drug by primary system organ class and preferred term

The presentation of “All AEs”, as described in [Section 2.11.3](#) (Adverse events by primary SOC and PT), will be repeated as relevant for those patients with AEs considered to be related to study drug.

An AE will be considered related to study drug if the response to the question “Reasonable possibility that AE is related to study drug?” as recorded in the Adverse event eCRF is:

Yes, investigational treatment.

Yes, both and/or indistinguishable.

2.11.5 Serious adverse events by primary system organ class and preferred term

The presentations described in [Section 2.11.4](#) (Adverse events related to study drug by primary SOC and PT) will be repeated as relevant for those patients with SAEs (excluding

death). An adverse event will be considered serious if the response to the question “Does AE meet the definition of an SAE?” = “yes”, as recorded in the Adverse event eCRF.

Specifically, SAEs leading to death will be summarized in a separate table, for each treatment group and “Active Total: Safety” as relevant, overall and by region (Japan/Non-Japan) (see [Section 2.6](#) [Subgroups]), displaying SOC and PT. An SAE will be considered leading to death if the reported outcome = “Fatal” on the Adverse event eCRF. Incidences will be calculated relative to the number of patients in SAF analysis set, or ongoing at the start of follow-up (“at risk”). Additional information reported on the Death eCRF such as date of death, if an autopsy was performed, the primary (including specification) and any other contributing reasons for death will be presented in a by-patient data listing sorted by Japan first and then by patient identifier.

2.11.6 AEs of special interest (AESI) – Liver/Diarrhea or diarrhea-like/Muscle contraction/Cardiac safety and Orthopedic events

The AEs of special interest include the following, specified as compound-level risk factors defined in the CRS and will be selected on Novartis MedDRA query (NMQ) or standardized MedDRA query (SMQ) based on the latest MedDRA version code level:

- Involuntary muscle contractions: Involuntary muscle contractions [BYM338] customized MedDRA query (CMQ) (NMQ) [narrow].
- Acne: Dermatologic toxicities [DOVITINIB] (CMQ) (NMQ) [narrow].
- Effects on cardiac function, conduction or perfusion: Effects on cardiac function, conduction or perfusion [BYM338] (CMQ) (NMQ) [narrow].
- Effect on hormones - Effect on hormones [BYM338] (CMQ) (NMQ) [narrow].
- Teratogenicity: Teratogenicity [BYM338] (CMQ) (NMQ) [narrow].
- Hypersensitivity: Hypersensitivity (SMQ) [narrow].
- Effect on bone fracture healing: Effect on bone fracture healing [BYM338] (CMQ) (NMQ) [narrow].
- Pericardial effusion, peripheral edema, and orthostatic hypotension: Pericardial effusion, peripheral edema, and orthostatic hypotension [BYM338] (CMQ) (NMQ) [narrow].
- Liver Toxicity: Drug related hepatic disorders - comprehensive search (SMQ) [narrow].
- Carcinogenicity: Carcinogenicity [BYM338] (CMQ) (NMQ) [narrow].
- Abuse potential: Drug abuse, dependence and withdrawal (SMQ) [broad].
- Diarrhea - Diarrhea [BYM338] (CMQ) (NMQ) [narrow].

The following actual exposure-adjusted (rate in 100 person-years) treatment-emergent AESIs regardless of study drug relationship by risk search criteria level (based on the NMQs or MedDRA SMQs) will be summarized for each treatment group and “Active Total: Safety”, overall and by region (Japan/Non-Japan) (see [Section 2.6](#) [Subgroups]). Percentages (%) will be derived relative to the number of patients “at risk” (in SAF or ongoing at the start of follow-up).

Additional data for adverse events of special interest (AESIs) related to liver, diarrhea spontaneous muscle contractions, orthopedic and heart/cardiomyopathy complications will be recorded, by the investigators, in the Liver event - overview eCRFs, Diarrhea or diarrhea-like

events eCRF, Spontaneous muscle contractions eCRF, Orthopedic complication eCRF, Heart failure eCRF and Cardiomyopathy eCRF respectively. This patient information will be summarized descriptively for all patients assigned to SAF analysis set, or who are ongoing at the start of follow-up (“at risk”).

Liver events

For treatment-emergent and post-treatment liver events, descriptive statistics (see [Section 3.2](#) [Precision and summary statistics]) will be presented based on high-level information in the Liver event – overview eCRF, Liver event - history of alcohol use 6 weeks prior to liver event eCRF and Liver event - drugs of abuse history eCRF:

- Number of treatment-emergent and post-treatment liver events (E).
- Type of liver injury:
 - Acute.
 - Acute on chronic liver disease.
 - Chronic.
- Liver failure present (yes/no).
- Tattoos in the last year (yes/no).
- Was the liver injury associated with any clinical signs/symptoms (yes/no).
- Any reasonable possibility that the liver event is related to study drug:
 - No.
 - Yes, investigational treatment.
 - Yes, other study drug (non-investigational).
 - Yes, both and/or indistinguishable.
- Did the patient discontinue study drug (yes/no).
- History of alcohol use (based on a “yes” response to the question, “Did subject use alcohol within the last 6 weeks?” on the History of alcohol use 6 weeks prior to liver event eCRF) presenting the amount of consumed alcohol (on average) by the following categories:
 - < 1 drink per day.
 - ≥ 1 to ≤ 2 drinks per day.
 - > 2 to ≤ 3 drinks per day.
 - > 3 to ≤ 4 drinks per day.
 - > 4 to ≤ 5 drinks per day.
 - > 5 drinks per day.
- History of drug abuse (based on a “yes” response to the question, “Did subject abuse any drugs within the last 6 months?” on the Drugs of abuse history liver event – eCRF):
 - Yes.
 - No.

Percentages (%) will be derived relative to the total number (E) of liver events with data available per question.

Diarrhea or diarrhea-like events

For treatment-emergent and post-treatment diarrhea or diarrhea-like events, descriptive statistics (see [Section 3.2](#) [Precision and summary statistics]) will be presented for the

characteristics as recorded in the Diarrhea or diarrhea-like events eCRF, or via the AESI search defined in the CRS:

- Number of treatment-emergent and post-treatment diarrhea or diarrhea-like events (E).
- Characteristics of the diarrhea events:
 - Daily average number of bowel movements during each event.
 - Softening of stool.
 - Watery.
 - Other.
- Diarrhea associated events:
 - Abdominal pain.
 - Nausea.
 - Vomiting.
- Daily average number of bowel movements during each event.
 - 1
 - 2 – 4
 - ≥ 5
 - Unknown

Percentages (%) will be derived relative to the total number of diarrhea or diarrhea-like events (E) with data available.

Muscle contraction events

For events of spontaneous muscle contractions, descriptive statistics (see [Section 3.2](#) [Precision and summary statistics]) will be presented for the characteristics as recorded in the Spontaneous muscle contractions eCRF. These are:

- Number of treatment-emergent and post-treatment events (E).
- The characterization of the episode:
 - Single contraction.
 - Series of contractions.
- Frequency of the episode(s):
 - Single episode, once a day.
 - Several episodes a day.
 - Irregularly over the weeks.
- The maximum pain severity.
- Part of the body affected:
 - Contraction of head/face.
 - Contraction of chest or ribcage.
 - Contraction of back.
 - Contraction of abdomen.
 - Contraction of the back of the thigh.
 - Contraction of front of the thigh.
 - Contraction of calf.
 - Contraction of feet.
 - Contraction of arms.

- Contraction of hands.
 - Other contractions.
- Did the event stop spontaneously (yes/no).
- The average duration of an episode:
 - 1 to 5 (sec).
 - 6 to 60 (sec).
 - > 1 to 10 (min).
 - > 10 to 60 (min).
 - > 1 to 24 (hours).
 - > 24 (hours).
- The level of physical activity at the time of the contraction:
 - Standing/walking.
 - Sitting/resting.
 - During or shortly after an exercise session.
 - In bed and not yet asleep.
 - Asleep.
- The existence of pain or not during the contraction (yes/no).
- The association of the contraction:
 - Uncontrolled movement of joint(s).
 - Abnormal bending of the affected joint(s).
 - Inability to open or relax hands after making a fist.
- The part of the body that was affected:
 - Head/face (yes/no).
 - Chest or ribcage (yes/no).
 - Back (yes/no).
 - Abdomen (yes/no).
 - Back of the thigh (yes/no).
 - Front of the thigh (yes/no).
 - Calf (yes/no).
 - Feet (yes/no).
 - Arms (yes/no).
 - Hands (yes/no).
 - Other (yes/no).
- If the event stopped spontaneously ([yes/no], if “no” then were any of the following medications or non-drug therapies administered to treat the event?):
 - Stretching and massaging (yes/no).
 - Hydration (yes/no).
 - Heat/cold (yes/no).
 - Analgesics (yes/no).
 - Muscle relaxant agent (yes/no).
 - Other (yes/no).

Percentages (%) will be derived relative to the total number of muscle contraction events (E) with data available per question.

Cardiac safety events

The frequency of patients experiencing at least one treatment-emergent or post-treatment cardiac event (cardiomyopathy, ischemic heart disease, heart failure, or cardiac rhythm disturbances [brady/tachyarrhythmias]) will be summarized in separate tables for each treatment group and “Active Total: Safety”, overall and by region (Japan/Non-Japan) (see [Section 2.6](#) [Subgroups]). Percentages (%) will be derived relative to the number of patients “at risk” (in SAF analysis set, or who are ongoing at the start of follow-up).

If the number of cardiac safety events are sufficient (based on events confirmed ($\geq 10\%$), the odds ratio, associated 95% confidence interval and p-value for the difference between each of the active bimagrumab treatment groups as well as “Active Total: Safety” and placebo will be analyzed using PROC FREQ. This analysis will be based on the proportion of patients with at least one treatment-emergent or post-treatment cardiac event (based on events [E] confirmed by adjudication committee) (see [Section 3.11.8](#) [Odds ratios]). Incidence calculations will be based on the number of patients with at least one cardiac safety event relative to the number of patients in SAF analysis set, or who are ongoing at the start of follow-up (“at risk”).

In addition, provided again that there are a sufficient number of events ($\geq 10\%$ of patients have at least one event), the time to the first cardiac event over the course of the study (as calculated relative to the start of first infusion of study drug) will be estimated for each treatment group and “Active Total: Safety”. Kaplan-Meier estimates for median time to first cardiac event with 95% confidence interval, 25th and 75th percentiles will be presented. Patients not experiencing a cardiac event will be censored at the time of study completion, premature discontinuation or if ongoing in the study at the last available assessment date. The survival distributions of time to first cardiac event will be compared between each active bimagrumab treatment group, “Active Total: Safety” and placebo by means of the log-rank statistic (see [Section 3.11](#) [Statistical methodology and assumptions]).

As the number of cardiac rhythm disturbance, heart failure, ischemic heart disease and cardiomyopathy events are expected to be low, descriptive statistics (see [Section 3.2](#) [Precision and summary statistics]), will be performed on the questions listed in the Cardiac rhythm disturbances, Heart failure, Ischemic heart disease and Cardiomyopathy eCRFs. Any information recorded in the Adverse events eCRF for an AE which is deemed to have an AE classification of “Cardiac rhythm disturbances”, “Heart failure”, “Ischemic heart failure” or “Cardiomyopathy” will also be summarized descriptively, if relevant.

Orthopedic events

Orthopedic events (i.e. fracture healing complications) will be summarized in a similar manner as the cardiac safety events described above. These events are expected to be rare and orthopedic information is recorded in the Orthopedic complications eCRF.

Hospitalizations

Hospitalizations will be summarized in a similar manner as the orthopedic/cardiac safety events described above. Descriptive statistics (see [Section 3.2](#) [Precision and summary statistics]) will be presented for certain characteristics as recorded in the Hospitalization eCRF. These are:

- Number of patients hospitalized and number of hospitalization events (E).

- Reasons for hospitalization:
 - Injurious fall with fracture.
 - Other.
- Place of discharge:
 - Home.
 - Long-term care facility.
- Average duration of hospitalizations (days) = Duration of hospitalization (Date of discharge – date of admission) / Number of hospitalizations.

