3.6 Risks and benefits

Risks

The safety data from the completed Phase I and II studies do not highlight any specific safety risk or concern or any particular pattern of major adverse event clustering. From the standpoint of the overall risk-benefit assessment, the current study design and its trial-related risks (e.g., infusion, blood draws, exposure to radiation during imaging) with bimagrumab are justified.

As of 1st September 2017 approximately 1341 adults have been enrolled in clinical trials with bimagrumab of which approximately 900 have received the antibody as study medication. Cumulatively, a total of 556 adults have participated or are participating in the Phase I program, with approximately 361 subjects having received bimagrumab. Seven-hundred eighty-five patients participated or are actively participating in the Phase II/III program. Dose [REDACTED]

levels have ranged from 0.01 mg/kg to 30 mg/kg as i.v. infusions and 2 mg/kg s.c. injections, with the majority receiving repeat doses of 10 mg/kg (equivalent to 700 mg) and 30 mg/kg i.v. bimagrumab. The current **safety profile** suggests that bimagrumab is well-tolerated with adverse events limited to minor, transient clinical symptoms. Transient cases of episodic, spontaneous muscle contractions, acne and diarrhea of mostly mild intensity have been observed in study participants with symptoms occurring more frequently in those participants receiving the highest doses of drug (30 mg/kg).

Preliminary data from the first studies in healthy volunteers and older patients indicate observations of diffuse acne on the face and less frequently on the back and chest in some adults receiving a single dose of 30 mg/kg. Treatment has been successful with good skin hygiene using a 4-10% benzoyl peroxide wash and over the counter topical treatments. On occasion, a prescription, topical or oral antibiotic (i.e., minocycline 100 mg bid), was used. The mechanistic link between bimagrumab and acne remains poorly understood. There were no relevant changes in total testosterone or testosterone-estrogen ratio to bimagrumab treatment that otherwise could have explained the skin findings (CBYM338X2108).

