As of 1 Sep 2017, there have been two confirmed cases of acute pancreatitis among the 642 study participants from completed studies and an estimated 250 participants in ongoing (blinded) studies administered bimagrumab. There is no association of the temporary elevations in lipase and/or amylase with an increased risk for pancreatitis.

In order to fully evaluate these new safety findings, additional safety monitoring measurements are added. Safety monitoring guidance for patients who experience elevated lipase and/or amylase during the study is provided in [Section 7.4](#).

Trial related risks

Infusion related reactions can occur with monoclonal antibodies. Hypersensitivity reactions can manifest as fever, chills, urticaria, dyspnea, headaches, myalgia and/or hypotension. A serious infusion reaction that results in anaphylaxis is a rare event in monoclonal antibody therapy. If a severe hypersensitivity reaction occurs, administration of bimagrumab must be discontinued and appropriate therapy initiated.

During the collection of blood samples, patients may experience pain and/or bruising at the insertion site of the needle/catheter. Although rare, localized clot formation, infections and nerve injury may occur. Lightheadedness and/or fainting may also occur during or shortly after the blood draw. Patients will be observed following all blood draws and discharged only when the Investigator observes stable health status. In addition, liquids by mouth in the form of water, fruit juice or a similar product will be provided following the blood draw to replenish the volume taken.

Radiation Exposure

This clinical study involves exposure to radiation from X-ray and DXA total body and contralateral (unaffected) hip scans. X-ray assessments at baseline and 6 months are part of standard medical care after hip fracture surgery. However, exposure at 9 and 12 months is usually not medically necessary. DXA radiation exposure is not necessary for medical care and it is intended for research purposes only. The total amount of radiation exposure per patient from X-ray and DXA scans will be about 3.65 mSv (365 mrem).

For effective radiation doses between 3 mSv (300 mrem) and 50 mSv (5000 mrem), the risk is considered to be "minimal". Therefore, the radiation exposure in this study involves minimal risk and is necessary to obtain the research information desired ([Stabin 2013](#)).

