7.4 Lipase and amylase elevations

To ensure patient safety and enhance the reliability in determining the potential for pancreatic events with bimagrumab, a standardized process for identification, monitoring and evaluation of pancreatic events has to be followed ([Table 7-2](#)).

[figure not shown]

Table 7-2 Safety monitoring guidance for amylase and lipase elevations

Event	Follow up monitoring
Lipase and/or amylase < 3x ULN	
 • If asymptomatic, follow up at discretion of investigator. • If clinical symptoms (e.g., abdominal pain, nausea, diarrhea) suggest pancreatic involvement, re-check enzymes (amylase, lipase) and inflammatory markers (C-reactive protein) and consider pancreatic imaging (i.e., abdominal ultrasound or CT or MRI) to evaluate for presence of pancreatitis.
Lipase and/or amylase ≥ 3x ULN	
 • Re-check enzymes (amylase, lipase) and inflammatory markers (C-reactive protein) independent of presence of clinical symptoms. • Assess subject for clinical symptoms. • Conduct pancreatic imaging (i.e. abdominal ultrasound or CT or MRI) to evaluate for presence of pancreatitis. • Study drug interruption based on findings of additional assessments and at discretion of investigator.

As defined in [Section 7.1](#), medically significant events which are considered as serious adverse events (SAEs) should follow the standard procedures for SAE reporting as described in [Section 7.2](#). Every pancreatic event reported as an SAE should include a causality assessment of the event via exclusion of alternative causes (e.g., gallstones, co-medication).

An investigation of the pancreas needs to be followed up until resolution. A gastroenterology consult can be included at the investigator’s discretion. All follow-up information, and the procedures performed, should be recorded in the appropriate CRFs.

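### SAP 2.11.6 retrieves the Acne AESI with a wider, differently tagged skin query and has no grouped pancreatic search: minor, and cheap to settle before unblinding

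*SAP*

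**What the plan says.** SAP 2.11.6 describes its events of special interest as "specified as compound-level risk factors defined in the CRS", the CRS being the programme's case retrieval sheet, which is not among the documents. Most entries use a customised query tagged for the study drug, for example "Involuntary muscle contractions: Involuntary muscle contractions [BYM338] customized MedDRA query (CMQ) (NMQ) [narrow" and "Diarrhea - Diarrhea [BYM338] (CMQ) (NMQ) [narrow". The acne entry is "Acne: Dermatologic toxicities [DOVITINIB] (CMQ) (NMQ) [narrow". The searches feed a table of treatment-emergent events per 100 person-years, which "by risk search criteria level (based on the NMQs or MedDRA SMQs) will be summarized for each treatment group".

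Acne is a named effect of the drug. Protocol 3.6 groups it with muscle contractions and diarrhea and reports "observations of diffuse acne on the face and less frequently on the back and chest" in some adults given a single 30 mg/kg dose.

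On the pancreas, Protocol 3.6 describes dose-dependent, transient, sub-clinical lipase and amylase elevations and states that "there have been two confirmed cases of acute pancreatitis among the 642 study participants" from completed studies and an estimated 250 in ongoing blinded ones. Protocol 7.4 sets up a standardised monitoring process to "enhance the reliability in determining the potential for pancreatic events with bimagrumab". The SAP version history says the document was revised for Amendment 4, which introduced that process. No search in SAP 2.11.6 names the pancreas.

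**The concern.** A grouped search is useful only if its terms match its label. A query titled for skin toxicity in general may bring in rashes and other skin events. Reported as acne, these could blur any relation with dose. Acne depends on this row more than the two effects named beside it. Muscle contractions and diarrhea have their own BYM338 queries, a place in the special-interest tables of SAP 2.11.3 and dedicated eCRF summaries. Acne has none of these, so the exposure-adjusted row is its only grouped analysis.

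For the pancreas, the protocol asks for events, and not only enzymes, to be identified and evaluated in a standard way. Protocol 9.5.2.3 plans counts by arm, with rates and 95% confidence intervals, for risks defined in the case retrieval strategy. A risk with no search does not reach that table. For a rare event, the set of terms that counts as a case is best fixed before the arms are known, because a set chosen afterwards is open to challenge.

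**Working it through.** The plan states no figure to reproduce. The check is a count of the list, a trace of the two risks through the tables, and one calculation for scale.

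**1. The list in SAP 2.11.6, by type of query**

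| Type | Entries | Number |
|---|---|---|
| Tagged BYM338 | muscle contractions; cardiac function; hormones; teratogenicity; fracture healing; pericardial effusion, edema and orthostatic hypotension; carcinogenicity; diarrhea | 8 |
| Standardised MedDRA query | hypersensitivity; liver toxicity; abuse potential | 3 |
| Other product tag | acne | 1 |
| Pancreatic | none | 0 |

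Total: 8 + 3 + 1 = 12. The documents do not define the tag on the acne entry. That it denotes another compound is inferred from its position, where the other customised queries show BYM338.

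**2. Where each risk is counted**

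- *Acne:* by preferred term, n and % by arm, in SAP 2.11.3, and again for related events in 2.11.4. Grouped and exposure-adjusted only through the query above.
- *Pancreatic enzymes:* Protocol 9.5.2.4 plans a summary of enzyme abnormalities. SAP Table 3.6 (section 3.8) sets five criteria: lipase and amylase each above 2 x ULN, each at or above 3 x ULN, and either or both at or above 3 x ULN. SAP 2.11.7 tabulates newly occurring notable values by arm on treatment, in follow-up and over the whole study.
- *Pancreatitis as an adverse event:* by preferred term in SAP 2.11.3, and in the related-event and SAE tables of 2.11.4 and 2.11.5. No grouped, exposure-adjusted row.

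**3. Scale for pancreatitis**

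Assumption: the programme's crude proportion applies here, whatever the differences in dose, duration and population. The active arms are planned at 70 + 70 + 35 = 175 patients (SAP 2.13). The programme denominator is 642 + 250 = 892. The 250 is an estimate, so 642 alone is shown as the other end of the range.

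Expected cases = 175 × p. Chance of at least one = 1 − (1 − p)^175.

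| p | Expected cases | Chance of at least one |
|---|---|---|
| 2/892 = 0.22% | 0.39 | 32% |
| 2/642 = 0.31% | 0.55 | 42% |

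No such calculation is possible for acne, because neither document gives the query's terms.

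**The case against.** A reader might infer four stronger things, none of which the documents support.

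- *That pancreatic risk is not analysed.* Enzyme abnormalities are tabulated by arm against five criteria, and any pancreatitis case appears by arm in the general AE and, if serious, SAE tables. Protocol 7.4 is monitoring guidance for sites and promises no special-interest analysis. Lipase and amylase guidance is also only one of the two purposes stated for Amendment 4. The other is to align the statistics section with the SAP.
- *That acne is miscounted.* This rests on a query title. The search is restricted to narrow scope, its terms may turn out to be close to acne, and reusing a query is not in itself an error. Acne is counted under its own preferred term in any case.
- *That the list is closed.* SAP 2.11.6 says that the events of special interest include those listed, and it defers to a retrieval sheet that cannot be seen here.
- *That a real signal would be lost.* Protocol 3.6 describes the acne after 30 mg/kg, whereas the top dose here is 700 mg, which the protocol equates to 10 mg/kg. It also states that the enzyme elevations are not associated with a higher risk of pancreatitis. With zero or one case likely, a grouped row adds little to the preferred-term tables.

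All of this stands and keeps the point small. It does not explain why a row labelled acne uses a query whose title says something broader. Nor do the preferred-term tables give a grouped or exposure-adjusted rate.

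**Conclusion.** Two limited findings hold. First, the label and the query of the acne row do not match on their face, so the exposure-adjusted acne rate by arm may not measure acne. The size and direction of any error are unknown without the term list. Second, pancreatic events have no grouped, exposure-adjusted rate by arm, although the enzyme values and individual preferred terms are reported. If the programme proportion applies, 0.39 to 0.55 pancreatitis cases would be expected in 175 active patients, so the second finding concerns pre-specification more than information lost.

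Both rest on the list as printed in SAP 2.11.6, since the retrieval sheet is not available. If that sheet already defines acne narrowly or holds a pancreatic search, the SAP text only needs to be brought into line with it. No efficacy inference is affected and no safety data are hidden. Priority: minor.

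**What to change.** Before unblinding:

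1. Define the acne AESI by acne and acneiform preferred terms in a BYM338 query, and list those terms. Alternatively, keep the present query and relabel the row to match it, leaving acne itself to the preferred-term table.
2. As an inexpensive improvement, add a pancreatic-event search to SAP 2.11.6 (a standardised acute pancreatitis query or a BYM338 query), reported with the same rates by arm. Show it beside the already planned incidence of lipase and/or amylase at or above 3 x ULN. If the retrieval sheet deliberately has no such search, say so and point to the laboratory and preferred-term tables.

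The cost is one update of the retrieval sheet, one table rerun and one more row. The added row will probably hold very few events, so it should be presented descriptively and not read as evidence that the arms are alike.
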